Study Protocol

**Digital Dyadic Empowerment Program on Lifestyle
Modification for Chronic Kidney Disease Management**

Official Title for Year 4 Study:

**Digital Dyadic Empowerment Program (DDEP) on Lifestyle Modification
for Chronic Kidney Disease Management: A Randomized Controlled Trial**

ID: NHRI-EX114-11106PI

NCT06756113

Responsible Party:

Principal Investigator: [name] [[name]]

**Official Title: Professor, Department of Nursing,
College of Medicine**

Affiliation: National Cheng Kung University

Collaborators:

National Health Research Institutes, Taiwan

Document Date: December 13th, 2024

Digital Dyadic Empowerment Program (DDEP) on Lifestyle Modification for Chronic Kidney Disease Management: A Randomized Controlled Trial

Objective

The purpose of this randomized controlled trial is to examine the synergistic long-term effects of the Digital Dyadic Empowerment Program (DDEP) compared to routine care among patients with chronic kidney disease (CKD). Specifically, the study aims to evaluate the program's impact on patients' kidney function, health-promoting lifestyle behaviors, and the dyads' relationship quality over time.

Design

A randomized controlled trial (RCT) will be conducted to test the effect of the Digital Dyadic Empowerment Program (DDEP) compared to routine care, with a single follow-up assessment at 6 months post-baseline. This RCT will adhere to the Consolidated Standards of Reporting Trials (CONSORT) 2010 statement ([Moher et al., 2010](#)) and the CONSORT-EHEALTH guidelines for digital health intervention evaluation ([Eysenbach & CONSORT-EHEALTH Group, 2011](#)) to ensure rigorous reporting and transparency in the study design and outcomes.

Participants

Patients aged over 20 years and diagnosed with CKD at stage 1 to 5 for at least six months will be recruited with the following inclusion criteria: (1) patients can identify a helpful significant other, and both parties are willing to participate; (2) patients are able to communicate in Mandarin or Taiwanese. Patients will be excluded if (1) the significant other is a health care provider, (2) either the patient or significant other has a known mental illness diagnosis, (3) the patient is currently receiving renal replacement therapies, or (4) neither the patient nor the significant other uses a smartphone or the LINE messaging app. Patients who

do not meet the smartphone or LINE app requirement will be excluded, as they would be unable to receive the intervention in the experimental group, ensuring rigorous randomization.

Setting

Subject will be recruited from outpatient clinics from a medical center in Southern Taiwan.

Sample Size

The estimated number of dyads will be based on the results of the Year 3 feasibility study, as a reference for calculating the effect and the rate of sample lost to follow-up. In the feasibility study, 60 dyads were recruited, and 55 completed the 3-month follow-up, resulting in a retention rate of 91.67%, which exceeds the 12-month retention rate of 64% reported by [Teng and colleagues \(2013\)](#) in a lifestyle modification program. For the formal RCT, the follow-up period has been shortened to 6 months. Efforts will be made to minimize attrition, targeting a dropout rate below 10%. Power analysis calculations, using G*Power software, indicate that for an effect size of 0.25 and a power of 0.8, a sample size of 76 dyads would be required. Adjusting for a 10% dropout rate, 84 dyads would be needed. To further safeguard against potential attrition and maintain robust subgroup analyses, the target recruitment will be 104 dyads. Considering the recruitment efficiency demonstrated in the feasibility study, the plan to recruit 104 dyads remains feasible and appropriate to ensure sufficient power for detecting intervention effects.

Measurements

Data collection will consist of the following instruments: Demographics (e.g., age, gender, education level) and Disease Related Characteristics (e.g., estimated glomerular filtration rate [eGFR], CKD stage), TTM staging Inventory, Dyadic Adjustment Scale-7 (DAS-7), and Health Promoting Lifestyle Profile-II Chinese version revised (HPLP-IIICR).

Procedure

Patients who meet the inclusion criteria will be referred to the study by nephrology outpatient clinic physicians at the study site. Patients attending their routine clinic visit to the nephrology clinic will be identified as potential subject if they meet the inclusion criteria. Dyads will be randomly assigned to either the experimental group or the control group using a pre-generated randomization list prepared via R programming's sample function and by a research assistant.

After assignment, the dyads will proceed to baseline assessment, which will include collecting demographic information, TTM stage of change, and other selected measures such as DAS-7 and HPLP-IICR. The dyads will complete the instruments in a private room, requiring approximately 15 minutes. Dyads assigned to the intervention group will receive the DDEP revised based on findings from year 3. This intervention will include the installation and usage of a digital platform to facilitate health-promoting behaviors and monitor outcomes. Control group participants will receive routine care without access to the DDEP platform during the study period but may join the platform after the study concludes.

Outcome measures will be evaluated at baseline (T0) and six months post-baseline (T1). Participants will be compensated with a small gift after completing each data collection session.

Data Analysis

Descriptive statistics will be conducted to summarize demographic and clinical characteristics. For ordinal outcome variables, such as CKD stage and TTM stage of change, Fisher's exact test will be used to examine the association between group assignment and pre-to-post change categories (e.g., reverse, maintain, or progress for CKD; advance, maintain, or regress for TTM).

Generalized Linear Mixed Models (GLMM) will be used to analyze differences between groups on continuous outcome indicators, considering the repeated-measures design of the study (Sharpe & Cribbie, 2023). The fixed effects in the models will include measurement time point (baseline and 6 months) and the interaction of group assignment (experimental vs. control) with time point, while random effects will include intercepts and time points to account for individual variability. Missing data will not be imputed. Analyses will be performed using IBM SPSS Statistics software (version 25.0). Statistical significance will be determined using a two-tailed p -value of < 0.05 .

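### Baseline self-reports are collected after assignment with no blinding described, and the plan describes neither allocation concealment nor balancing on CKD stage.

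*Combined protocol and SAP*

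**What the plan says.** All references are to the combined protocol and SAP.

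- **Procedure, allocation.** "Dyads will be randomly assigned to either the experimental group or the control group using a pre-generated randomization list". The same sentence describes this as a "pre-generated randomization list prepared via R programming's sample function and by a research assistant". The available text gives no allocation ratio, blocks or strata. It does not say who holds the list, whether recruiters are kept from it, or how each assignment is released.
- **Procedure, order of events.** "After assignment, the dyads will proceed to baseline assessment". That assessment includes TTM stage of change, DAS-7 and the health-promoting lifestyle profile.
- **Participants.** Patients are eligible if "diagnosed with CKD at stage 1 to 5 for at least six months", so stage is already on record when a dyad is assigned.
- **Setting and Sample Size.** One medical center; "the target recruitment will be 104 dyads".
- **Data Analysis.** For CKD stage and TTM stage, "Fisher's exact test will be used to examine the association between group assignment and pre-to-post change categories". Continuous outcomes go into a GLMM whose listed fixed effects are time and group by time. CKD stage is not a listed covariate, and no imputation is planned.
- **Design.** The trial commits to CONSORT 2010 and CONSORT-EHEALTH. The available text does not mention blinding.

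**The concern.** A baseline is useful as a reference only if it cannot depend on the arm. Here the stated order puts it after assignment. A dyad that has just learned it will get the programme may describe its habits, readiness to change or relationship differently from one that has learned it will not. A disappointed dyad may decline the questionnaires altogether. Either would enter the analysis as if it were a pre-treatment difference.

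The rest of the allocation procedure gives no visible protection. Entry leaves room for judgement: physicians refer, the patient must name a helpful significant other, and both must be willing. If whoever approaches dyads could see the next line of the list, that judgement could follow the coming assignment, and later adjustment could not reliably repair it.

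CKD stage also matters for the kidney outcome. On the reverse/maintain/progress scale a stage 1 patient cannot reverse and a stage 5 patient cannot progress. Starting stage therefore limits which categories are open, and the planned test does not account for it.

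**Working it through.** The plan states no figure on this point, so there is none to reproduce.

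**1. Effect of a T0 shift on the continuous outcomes.** Let arm knowledge move mean T0 answers by δE in the experimental arm and δC in the control arm. The group-by-time contrast is

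(T1E − T0E) − (T1C − T0C),

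so its bias is −(δE − δC): one for one. The Data Analysis section lists no separate group main effect. If the model is fitted so that the baseline mean is common to both arms, the bias becomes −β(δE − δC), where β is the slope of T1 on T0. It disappears only if β = 0. The documents give nothing from which to size δE − δC, and its direction is not determined.

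**2. Effect on the TTM change categories.** Advance, maintain and regress are defined from the T0 stage. A patient who reports a later stage at T0 after hearing the assignment has less room to advance. A patient with no T0 stage cannot be classified.

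**3. Which outcomes are exposed.** DAS-7, the lifestyle profile and TTM stage are self-reported. eGFR and CKD stage are much less open to this effect.

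**4. Chance imbalance in CKD stage.** Inputs: 104 dyads (Sample Size); 52 per arm (assumed, as no ratio is stated); share in stages 4-5 of 30, 40 or 50% (assumed, as no distribution is given), which is K = 31, 42 or 52 patients of 104. With X the number of these in one arm, X is hypergeometric (104, K, 52), and the gap in share is |2X − K|/52.

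| Share in stages 4-5 | P(gap ≥ 10 points) | P(gap ≥ 15 points) | P(gap ≥ 20 points) |
|---|---|---|---|
| 30% | 0.198 | 0.085 | 0.031 |
| 40% | 0.318 | 0.161 | 0.027 |
| 50% | 0.327 | 0.170 | 0.030 |

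Under simple randomisation, simulation gives 0.28 to 0.31 for a gap of at least 10 points over the same shares, so the result hardly depends on how the list was drawn.

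**5. What an imbalance does to the Fisher comparison.** Assume progression of 30% in stages 4-5 and 10% in stages 1-3, with 42 of 104 in stages 4-5. A 15-point imbalance shifts the arm difference by 0.15 × (0.30 − 0.10) = 0.03, or 3 points. The overall rate is (42 × 0.30 + 62 × 0.10)/104 = 0.181. The standard error of the difference is √(2 × 0.181 × 0.819/52) = 0.075, or 7.5 points. The shift is thus less than half a standard error. Simulating this case with no treatment effect (20,000 shuffles of 52:52, progress versus not), the unadjusted Fisher test rejected in 2.7% of runs at nominal 5%. Type I error is not inflated.

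**6. After stratified blocking.** With blocks of 4 and 6 within two stage strata, the arms differ by at most 3 dyads in a stratum, so the gap in share is at most about 3/52 = 5.8 points.

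**The case against.** The strongest reply is that most of this is silence, not error. A reader might infer that the list is open to recruiters, or that allocation is unconcealed. The documents do not support that: they do not say who sees the list. The clause about the research assistant can mean that the assistant prepares the list, assigns dyads, or both. A list generated in advance is ordinary practice. Nor does the mention of R's sample function show that balancing is absent, since that function can also shuffle within blocks and strata. All of this stands, and the point is limited to what is not described.

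A reader might also infer that stage imbalance invalidates the CKD-stage comparison. It does not. Random imbalance is part of the Fisher test's null distribution, and for continuous outcomes the group-by-time contrast already removes level differences between arms. What is lost is precision. In addition, a split at stages 1-3 versus 4-5 does not separately balance stages 1 and 5, where the scale is truncated. This stands too, and it is why the analysis should adjust for starting stage as well.

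On baseline timing, the text fixes the order but does not say that dyads are told their arm before answering. Also, a reporting shift that was equal at T0 and T1 would cancel in a change score, and T1 self-reports remain exposed to arm knowledge whatever is done at T0. These points limit what can be claimed about size and direction. They do not justify keeping an order that permits the problem when the reverse order is available. The CONSORT commitment governs reporting and supplies no procedure.

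**Conclusion.** The concern holds as a low-cost improvement that should be made. The firm part is the stated order: T0 self-reports follow assignment, no blinding is described, and these values feed straight into the effect estimate and the TTM categories. The size of any distortion cannot be computed from the documents.

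Concealment and separation of roles are not described, so selection bias is a risk whose size is also unknown. No balancing on CKD stage is described either. With a 52:52 list and an assumed 30-50% in stages 4-5, a gap of at least 10 points is fairly likely (20-33%), and one of at least 20 points is rare (about 3%). That is a matter of precision and credibility, not of test validity.

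**What to change.** 1. Reverse the order in the Procedure section: complete consent and all T0 measures before the assignment is revealed to anyone.
2. State who generates the list, who holds it and who enrols. The holder should be an existing team member who does not recruit. Release each assignment by sequentially numbered opaque sealed envelope or an equivalent online step.
3. State the allocation ratio. Generate the list in permuted blocks of randomly varying size (for example 4 and 6), stratified by CKD stage (for example 1-3 versus 4-5).
4. Include the stratum in the outcome models. For CKD-stage change, replace the unadjusted Fisher test with a stage-stratified analysis or an ordinal analysis adjusted for baseline stage.

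The cost is a few lines of R, envelopes or an online release, and revised wording; no extra visits or dyads are needed. The downside is slightly more administration and a small risk of predictability from blocking, which varying the block size limits. If concealment or blocking is already in place, items 2 and 3 may need little more than writing it down.

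### Self-reported baselines (HPLP-IICR, DAS-7, TTM stage) are collected after randomisation, and nothing withholds the arm until they are complete

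*Combined protocol and SAP*

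**What the plan says.** The Procedure section of the combined protocol and SAP sets out this order:

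- Allocation: "Dyads will be randomly assigned to either the experimental group or the control group using a pre-generated randomization list". A research assistant is involved in the list.
- Baseline: "After assignment, the dyads will proceed to baseline assessment". The measures listed for that session are demographics, stage of change, DAS-7 and HPLP-IICR.
- Mode of completion: "The dyads will complete the instruments in a private room, requiring approximately 15 minutes".
- Experimental arm: "This intervention will include the installation and usage of a digital platform to facilitate health-promoting behaviors and monitor outcomes".
- Control arm: "Control group participants will receive routine care without access to the DDEP platform during the study period".

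Under Data Analysis, T0 is one of two time points in the GLMM. The treatment effect is read from "the interaction of group assignment (experimental vs. control) with time point". For TTM stage, T0 is the starting value from which each patient is classed as advancing, maintaining or regressing, and Fisher's exact test compares those classes between arms.

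The text available for review contains no statement on blinding of participants or assessors, on allocation concealment, or on delaying disclosure of the arm. The Design section commits to CONSORT 2010 and CONSORT-EHEALTH, but as reporting standards, and this sets no such safeguard.

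**The concern.** A baseline is useful in a randomised trial because the allocation cannot have influenced it. Here that protection is not secured. A dyad that knows it will get the platform, or knows it will not, may answer differently about its habits, readiness to change and relationship. Staff who know the arm could also influence the answers.

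The Objective section names kidney function, lifestyle behaviour and relationship quality. HPLP-IICR and DAS-7 carry the last two, so two of the three stated aims rest on exposed measures. Any arm-related shift at T0 passes into the estimated effect, its direction cannot be predicted, and once the data are collected no analysis can separate it from chance imbalance.

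A lesser point is that a dyad withdrawing between assignment and T0 would be randomised with no data at all. No rate for this is documented.

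**Working it through.** The plan gives no figure on this point, so there is nothing to reproduce. The order of events is stated in the text. The arithmetic below only shows how a shift at T0 would travel through the planned analyses.

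**Inputs from the protocol.** Target of 104 dyads and 10% dropout (Sample Size); two-sided 0.05 and two time points (Data Analysis).

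**Assumptions, not in the documents.**
- 1:1 allocation, so n = 104 × 0.9 / 2 = 46.8, taken as 47 per arm.
- Outcome SD of 1 at both times, and T0–T1 correlation ρ from 0.3 to 0.7.
- A shift b (in SD) in one arm's T0 mean, and no true effect.

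**Bias in the treatment contrast (absolute size).**

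| Shift at T1 | Unconstrained change contrast | T0 adjusted for, or T0 means constrained equal |
|---|---|---|
| None | b | about ρb |
| Same as at T0 | 0 | about (1 − ρ)b |

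The right-hand column matters because the listed fixed effects are time and group-by-time, with no group main effect. If the model is coded so that the T0 means are equal, it assumes exactly what this order of events puts in doubt. The text does not settle the coding.

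**Formulas, no shift at T1.**
- Change contrast: SE = √[(2/n) × 2(1 − ρ)], noncentrality b/SE, noncentral t on 2n − 2 df.
- Constrained contrast: estimate −ρb, SE = √[(2/n)(1 − ρ²)], normal approximation.

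**Worked case, b = 0.2 and ρ = 0.5.**
- Change: SE = √(2/47) = 0.206; 0.2/0.206 = 0.97; rejection probability 0.160.
- Constrained: estimate 0.5 × 0.2 = 0.1 in size; SE = √(2/47 × 0.75) = 0.179; 0.1/0.179 = 0.56; rejection probability 0.087.

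**Type I error, nominal 0.05, no shift at T1, ρ = 0.3 / 0.5 / 0.6 / 0.7.**

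| b (SD) | Change contrast | T0 means constrained equal |
|---|---|---|
| 0.1 | 0.069 / 0.077 / 0.084 / 0.095 | 0.053 / 0.059 / 0.065 / 0.076 |
| 0.2 | 0.128 / 0.160 / 0.189 / 0.236 | 0.061 / 0.087 / 0.112 / 0.158 |
| 0.3 | 0.229 / 0.302 / 0.363 / 0.459 | 0.074 / 0.134 / 0.193 / 0.297 |

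A simulated ANCOVA with T0 as covariate agrees closely with the right-hand column (for b = 0.3, from 0.07 to 0.28). With 38 per arm (76 dyads), the change-contrast ranges are 0.065–0.086, 0.112–0.199 and 0.194–0.385.

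**If the shift carries over to T1 (47 per arm).**
- Fully: the change contrast stays at 0.05. ANCOVA gives 0.07–0.11 for b = 0.2 and 0.09 to about 0.18 for b = 0.3.
- By half: the change contrast gives 0.069–0.095 for b = 0.2 and 0.093–0.153 for b = 0.3.

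**TTM change categories.** A latent normal variable was cut into five equally common stages (an assumption) and a 2 × 3 Fisher test applied, with no shift at T1 and ρ = 0.3 / 0.6 / 0.7:
- b = 0: 0.048 / 0.048 / 0.055
- b = 0.1: 0.053 / 0.069 / 0.074
- b = 0.2: 0.087 / 0.120 / 0.138
- b = 0.3: 0.129 / 0.194 / 0.238

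With an upward T0 shift of 0.3 SD and no true effect, the share classed as advancing falls from 37% to 28% (ρ = 0.3) or from 30% to 19% (ρ = 0.7).

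**The case against.** The strongest reply is that the protocol documents the sequence but not the disclosure. An assignment can be read from a list and kept from the dyad until the questionnaires are finished. That the arms look different shows what dyads know once the intervention starts, not what they know during the baseline session. This is fair: a biased baseline is not established. What is established is an order that permits one, with no stated safeguard against it.

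The second reply concerns size. The shift, the correlation, the allocation ratio and the TTM stage distribution are all assumed, and the largest figures need a shift that is present at T0, absent at T1 and analysed as plain change. Since T1 is also self-reported with the arm known, some persistence is plausible, and full persistence leaves the change analysis at 0.05. This also stands, and the range properly runs from no inflation to several-fold. However, a persistent shift moves the problem into the adjusted or constrained analysis, so neither form of analysis is safe under both patterns.

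Third, kidney function is the first-named aim and is not exposed, and the available text designates no primary outcome, so it cannot be shown that the main conclusion is affected. Withdrawal between assignment and T0 is speculative, more so if both happen at one visit. Both limits are accepted. They narrow the point but do not remove it for HPLP-IICR, DAS-7 and TTM stage.

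**Conclusion.** The concern holds. The protocol itself places randomisation before the self-reported baseline, and nothing in the available text keeps the arm from the dyads or from the staff collecting T0. The exposed analyses are the HPLP-IICR and DAS-7 group-by-time contrasts and the TTM change-category test.

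The size is unknown. Under the stated assumptions, a 0.1 SD shift does little harm (at most about 0.10 against a nominal 0.05). A 0.3 SD shift that is absent at T1 could bring the error to 0.23–0.46 in a change analysis and 0.07–0.30 in an adjusted or constrained one.

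The case for correcting it before enrolment does not depend on the upper figures. The bias cannot be diagnosed or removed afterwards, and preventing it costs almost nothing. Confidence is medium, because the protocol does not say when the arm is disclosed.

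**What to change.** Reword the Procedure so that eligibility and consent come first, all T0 instruments are then completed and locked, and only after that is the dyad's assignment drawn from the list and revealed.

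If the order must stay, the minimum is one sentence stating that neither the dyad nor the staff collecting T0 know the arm until T0 is locked.

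The protocol should also state as a remaining limitation that T1 self-reports are given with the arm known. Reordering does not cure that.

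The cost is one or two sentences and a change of order around a session of about 15 minutes. No patients, visits or staff are added, assuming assignment and T0 fall at the same visit, which the protocol does not contradict.

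### TTM stage is compared by an unordered Fisher test on three change categories that ignores baseline stage, which makes the comparison less sensitive than the data allow

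*Combined protocol and SAP*

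**What the plan says.** The Data Analysis section classes the outcome as ordinal ("For ordinal outcome variables, such as CKD stage and TTM stage of change") and then states that "Fisher's exact test will be used to examine the association between group assignment and pre-to-post change categories". For stage of change, the categories offered as examples are "advance, maintain, or regress for TTM". The section names no stratification or adjustment by baseline stage, and it gives no rule separating a participant who stays at the top stage from one who stays lower down. The mixed model in the same section is reserved for continuous outcomes, so this is the only between-group TTM analysis described.

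The Participants section admits any stage of change: "Patients aged over 20 years and diagnosed with CKD at stage 1 to 5 for at least six months will be recruited", with further criteria that do not concern TTM. Stage is measured at baseline and again at six months. The Procedure section places the first measurement after randomization: "After assignment, the dyads will proceed to baseline assessment". The Measurements section names the TTM instrument but not its number of stages or its scoring.

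**The concern.** A three-way change code discards two things that the trial will already have recorded.

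- **Starting point.** A top-stage participant has only two possible codes, *maintain* or *regress*. A lowest-stage participant has only *maintain* or *advance*. The same word, *maintain*, is the best attainable result for the first and no progress for the second.
- **Order and size.** Fisher's test treats the three categories as unordered labels, and a two-stage move counts the same as a one-stage move.

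What is at stake is the chance of detecting a real effect on stage of change, and how readable the result is. A reported *maintain* percentage does not by itself show how many participants were holding the top stage and how many never left the lowest.

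**Working it through.** **Figures in the plan.** No power figure is given for the TTM comparison. The 76, 84 and 104 dyads in the Sample Size section are not tied to this outcome, and the point does not depend on how 76 was obtained. Only the number of completers is taken from there: 104 × 0.90 = 93.6, so about 47 per arm if allocation is 1:1 (the ratio is not stated).

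**Assumptions not in the documents.** Five ordered stages. In controls, stage changes by −1, +1 or +2 with probability 0.20, 0.20 and 0.05 (no change 0.55), truncated at the ends. In the experimental arm, each participant ends one stage higher with probability *b*, capped at the top. Two-sided alpha is 0.05, as the plan states.

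**Step 1: is the pooling real?** Take an even baseline, 20% at each stage.
- Lowest-stage controls maintain with probability 0.55 + 0.20 = 0.75. Top-stage controls maintain with probability 0.55 + 0.20 + 0.05 = 0.80. Intermediate stages maintain with probability 0.55.
- Control *maintain* = 0.2 × 0.75 + 0.2 × 0.80 + 0.6 × 0.55 = 0.15 + 0.16 + 0.33 = 0.64.
- So 16% of controls held the top stage and 15% stayed at the lowest, under one code.

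**Step 2: where does a benefit go?** Same baseline, *b* = 0.5.
- *Advance* rises from 0.20 to 0.20 + 0.5 × (0.64 − 0.16) = 0.44.
- *Regress* falls from 0.16 to 0.5 × 0.16 = 0.08.
- *Maintain* becomes 1 − 0.44 − 0.08 = 0.48.

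The benefit is visible in the outer cells.

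**Step 3: power at *b* = 0.5, 47 per arm, 1,200 simulated trials per row.** Three tests are compared: the planned exact 2×3 Fisher test; a Wilcoxon test on the same three categories in order; and a van Elteren test, which ranks six-month stage within each baseline stage and combines the strata. At power 0.5 the simulation standard error is √(0.25/1200) = 0.014.

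| Baseline distribution | Fisher | Ordered 3 categories | van Elteren | Total gain (points) | Of which order |
|---|---|---|---|---|---|
| Even | 0.607 | 0.708 | 0.756 | 14.9 | 10.1 |
| Half top, half lowest | 0.516 | 0.618 | 0.786 | 27.0 | 10.2 |
| Top-weighted (40% top, 5% lowest) | 0.467 | 0.590 | 0.616 | 14.9 | 12.3 |
| Bottom-weighted (40% lowest, 5% top) | 0.776 | 0.839 | 0.852 | 7.6 | 6.3 |

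The remainder, from conditioning on baseline stage and keeping the size of the move, is 4.8, 16.8, 2.6 and 1.3 points. It is large only where participants sit at both extremes.

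**Step 4: weaker effect, *b* = 0.3, 1,500 trials per setting.** Fisher to van Elteren: even 0.252 to 0.333; half and half 0.227 to 0.348; top-weighted 0.193 to 0.256; bottom-weighted 0.358 to 0.441; concentrated in the middle 0.288 to 0.339; heavily top-weighted 0.132 to 0.172. Gains run from 4 to 12 points.

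**Step 5: no effect, *b* = 0.** Over the same six baselines Fisher rejects in 4.0% to 5.1% of trials and van Elteren in 4.1% to 5.5%. Neither shows false-positive bias.

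**Step 6: other assumed settings.** Further settings at 47 per arm included a latent-normal model with a 0.6 SD benefit and baseline-to-follow-up correlation 0.6. There, planned power of about 0.29 to 0.81 became about 0.54 to 0.96 with the stratified test, a gain of about 7 to 28 points. The weak-effect settings in step 4 fall partly below that range.

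**The case against.** The strongest reply is that the categories describe change correctly, that every change measure has a ceiling and a floor, and that randomization makes baseline stage comparable in expectation. All of that stands. There is no bias here and no scoring error, only an inefficient choice of analysis.

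A reader might go further than the point does and infer that a real benefit cancels inside *maintain*, with more top-stage holders offsetting fewer lowest-stage stayers. The *maintain* share can indeed stand still. In the latent model with 30% starting at the top and 20% at the lowest stage, it is 38% in controls and 37% in the experimental arm, while top-stage holders rise from 17% to 25% and lowest-stage stayers fall from 10% to 5%. But the planned test uses all three cells. In that same setting *advance* goes from 31% to 50% and *regress* from 31% to 13%. With identical *maintain* counts, 7/30/10 against 15/30/2 (advance/maintain/regress) gives Fisher p = 0.017. The comparison is less sensitive, not blind.

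It is also fair to say that the stakes are limited. The categories are introduced as examples, TTM stage is absent from the stated objective, and no section makes it primary. Some of the low power in a top-weighted sample is unavoidable, because those participants have no room to improve.

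**Conclusion.** The point holds as a loss of sensitivity. The plan calls the outcome ordinal and then analyses it as unordered, without the baseline stage that it collects. In the settings examined, the baseline-stratified ordinal test always had more power than the planned one: about 7 to 28 points in the wider set, and 4 to 12 points with the weaker effect in the stepwise model. In the step 3 settings, 6 to 12 points came from using the order of the categories alone.

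These sizes rest on assumed values for the number of stages, the baseline distribution, the pattern of change and the effect, plus 1:1 allocation. The direction was the same throughout; the amount cannot be fixed from the documents. The documents do not support describing this as bias, an inflated error rate or a hidden benefit. Severity is modest.

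**What to change.** Before data are seen, name one between-group analysis of six-month TTM stage: a proportional-odds model with arm and baseline stage as covariates, or a van Elteren test stratified by baseline stage. Report the stage-by-stage transition table for each arm, with counts for those who held the top stage and those who held the lowest. Keep the advance/maintain/regress table as description.

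The cost is a sentence or two in the Data Analysis section. No new data are needed, since both stages are already collected. There are two small downsides. The model brings a proportional-odds assumption, which the van Elteren test avoids. And because baseline stage is recorded after assignment, adjustment does not cure any difference between arms in how baseline is reported; the planned change categories share that weakness.

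A tempting alternative is to keep Fisher's test and recode the categories, counting a held top stage as favourable and a held lowest stage as unfavourable. It is less dependable: it gained 6 to 14 points under the latent model but only about −3 to +9 under the stepwise one, and it still ignores order and creates new mixtures of changed and unchanged participants.
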